## APPENDIX II: DEFINITIONS

The following definitions will be used in the SUMMIT trial Clinical Investigational Plan. All events constituting primary or secondary endpoints will be adjudicated by the independent Clinical Events Committee, along with relationship to the Treatment or Control group device and/or procedure.

### Bleeding

Bleeding is defined per MVARC, which is based on the modified VARC-2 and modified Bleeding Academic Research Consortium (BARC) [69]. For this trial, the CEC will adjudicate bleeding events based on the tables below.

MVARC Primary Bleeding Scale (Modified VARC-2)	
I. Minor	
Any overt, actionable sign of hemorrhage (e.g., more bleeding than would be expected for a clinical circumstance, including bleeding found by imaging alone) that meets <math>\geq 1</math> of the following:
 
 
• requiring nonsurgical medical intervention by a health care professional
 
• leading to hospitalization or increased level of care
 
• prompting evaluation; or requires 1 or 2 U of whole blood or packed RBC transfusion; and
 
• does not meet criteria for major, extensive, or life-threatening bleeding.
 

II. Major	
Overt bleeding either associated with:
 
 
• a drop in the hemoglobin of <math>\geq 3.0</math> g/dl or requiring transfusion of <math>\geq 3</math> U of whole blood or packed RBCs, and
 
• does not meet criteria of life-threatening or extensive bleeding.
 

III. Extensive	
Overt source of bleeding with:
 
 
• a drop in hemoglobin of <math>\geq 4</math> g/dl or whole blood or packed RBC transfusion <math>\geq 4</math> U within any 24-h period, or
 
• drop in hemoglobin of <math>\geq 6</math> g/dl or whole blood or packed RBC transfusion <math>\geq 4</math> U (BARC type 3b) within 30 days of the procedure.
 

IV. Life-threatening	
Bleeding in a critical organ, such as intracranial, intraspinal, intraocular, or pericardial necessitating surgery or intervention, or intramuscular with compartment syndrome OR bleeding causing hypovolemic shock or hypotension (systolic blood pressure <math><90</math> mm Hg lasting <math>>30</math> min and not responding to volume resuscitation) or requiring significant doses of vasopressors or surgery.

V. Fatal	
Bleeding adjudicated by the CEC as being a proximate cause of death. Severe bleeding adjudicated as being a major contributing cause of a subsequent fatal complication, such as MI or cardiac arrest, is also considered fatal bleeding.

### **Modified BARC Bleeding Scale (Secondary Use)**

#### **Type 0**

No bleeding.

**Type 1**

Bleeding that is not actionable and does not cause the patient to seek unscheduled performance of studies, hospitalization, or treatment by a health care professional. May include episodes leading to self-discontinuation of medical therapy by the patient without consulting a health care professional

**Type 2**

Any overt, actionable sign of hemorrhage (e.g., more bleeding than would be expected for a clinical circumstance, including bleeding found by imaging alone) that does not fit the criteria for type 3, 4, or 5 but does meet at least one of the following criteria:

- requiring nonsurgical, medical intervention by a healthcare professional
- leading to hospitalization or increased level of care, or
- prompting evaluation

**Type 3**

**Type 3a**

- Overt bleeding plus hemoglobin drop of 3 to  $<5$  g/dL\* (provided hemoglobin drop is related to bleed)
- Any transfusion with overt bleeding

**Type 3b**

- Overt bleeding plus hemoglobin drop  $\geq 5$  g/dL\* (provided hemoglobin drop is related to bleed)
- Cardiac tamponade
- Bleeding requiring surgical intervention for control (excluding dental/nasal/skin/hemorrhoid)
- Bleeding requiring intravenous vasoactive agents

**Type 3c**

- Intracranial hemorrhage (does not include microbleeds or hemorrhagic transformation, does include intraspinal)
- Subcategories confirmed by autopsy or imaging or lumbar puncture
- Intraocular bleed compromising vision

**Type 4 (periprocedural)**

- Perioperative intracranial bleeding within 48 h
- Reoperation after closure of sternotomy for the purpose of controlling bleeding
- Transfusion of  $\geq 5$  U whole blood or packed red blood cells within a 48-h period†
- Chest tube output  $\geq 2$  L within a 24-h period

**Type 5 (fatal bleeding)**

**Type 5a**

- Probable fatal bleeding; no autopsy or imaging confirmation but clinically suspicious

**Type 5b**

- Definite fatal bleeding; overt bleeding or autopsy or imaging confirmation

**Canadian Cardiovascular Society Grading of Angina Pectoris (CCS Angina Classification)**  
 CCS Angina Classification is defined by the Canadian Cardiovascular Society [79] as:

Grade	Definition
I	Ordinary physical activity does not cause angina, such as walking and climbing stairs. Angina with strenuous or rapid or prolonged exertion at work or recreation
II	Slight limitation of ordinary activity. Walking or climbing stairs rapidly, walking uphill, walking or stair climbing after meals, or in cold, or in wind, or under emotional stress, or only during the few hours after awakening. Walking more than two blocks on the level and climbing more than one flight of ordinary stairs at a normal pace and in normal conditions.
III	Marked limitation of ordinary physical activity. Walking one or two blocks on the level and climbing on flight of stairs in normal conditions and at normal pace.
IV	Inability to carry on any physical activity without discomfort, anginal syndrome may be present at rest.

### Cardiovascular Death

Cardiovascular death is defined by VARC II [80], as any one of the following:

- Death due to proximate cardiac cause (e.g., myocardial infarction, cardiac tamponade, worsening heart failure)
- Death caused by non-coronary vascular conditions such as neurological events, pulmonary embolism, ruptured aortic aneurysm, dissecting aneurysm, or other vascular disease
- All procedure-related deaths, including those related to a complication of the procedure or treatment for a complication of the procedure
- All valve-related deaths including structural or non-structural valve dysfunction or other valve-related adverse events
- Sudden or unwitnessed death
- Death of unknown cause

Non-cardiovascular death is any death in which the primary cause of death is clearly related to another condition (e.g., trauma, cancer, suicide).

### Causal Relationship (from ISO 5840-3)

Causal relationship is the relationship of the AE to the device, the implant procedure or the patient's condition. It should be established for both the Tendyne and Control device, based on the following categories:

Relatedness	Definition
Device-related	Any AE involving the function of the device, or the presence of the device in the body. Included in this category are events that are directly attributed to the device or the use of the device system.

Relatedness	Definition
Procedure-related	Any AE that results from the implant procedure. Events in this category are directly related to the general procedural sequelae.
Patient condition-related	Any AE that results from the worsening of a pre-existing condition or cannot be attributed to the device procedure.

### Chronic Kidney Disease

The following definitions of Chronic Kidney Disease will be utilized in the trial, as stated from National Institute for Health & Clinical Excellence [81]:

Stage	Definition
1	Slightly diminished function; kidney damage with normal or relatively high GFR ( $\geq 90$ mL/min/1.73 m  ). Kidney damage is defined as pathological abnormalities or markers of damage, including abnormalities in blood or urine test or imaging studies.
2	Mild reduction in GFR (60–89 mL/min/1.73 m  ) with kidney damage. Kidney damage is defined as pathological abnormalities or markers of damage, including abnormalities in blood or urine test or imaging studies.
3	Moderate reduction in GFR (30–59 mL/min/1.73 m  ). British guidelines distinguish between stage 3A (GFR 45–59) and stage 3B (GFR 30–44) for purposes of screening and referral.
4	Severe reduction in GFR (15–29 mL/min/1.73 m  ) Preparation for renal replacement therapy.
5	Established kidney failure (GFR <15 mL/min/1.73 m  ), permanent renal replacement therapy, or end stage renal disease.

### Coronary Artery Disease

Approximately two-thirds of patients with HF have underlying CAD (ischemic cardiomyopathy). Therefore, it is imperative that appropriate treatment for CAD be used in the SUMMIT trial, according to the ACC/AHA/HSFA Guidelines for Heart Failure. Specific recommendations listed in those guidelines are listed as follows:

- Use of nitrates and beta blockers for the treatment of angina,
- Coronary revascularization according to recommended guidelines in patients who have both HF and angina,
- Patients with coronary artery disease and HF should be treated in accordance with recommended guidelines for chronic stable angina,
- Use of antiplatelet agents for prevention of MI and death in patients with HF who have underlying coronary artery disease

In addition, revascularization (i.e., percutaneous coronary intervention, etc.) should occur prior to subject registration in the trial, as applicable.

## Endocarditis

Defined as a diagnosis of endocarditis based on the following Duke criteria [82]:

Criteria	Definition
Pathological Criteria	
 
• Microorganisms: culture or histology in a vegetation, in a vegetation that has embolized, or in an intracardiac abscess, or
 
• Pathological lesions: vegetation or intracardiac abscess present, confirmed by histology showing active endocarditis; or
 

Major Clinical Criteria	
 
• Persistently positive blood cultures: 
 
○ Typical organisms for endocarditis: Streptococcus viridans, S. bovis, “HACEK” group, community acquired Staphylococcus aureus or enterococci, in the absence of a primary focus
 
 
 
• Persistent bacteremia: 
 
○ ≥ 2 positive cultures separated by ≥12 hours or ≥ 3 positive cultures ≥ 1 h apart or 70% blood culture samples positive if ≥ 4 are drawn
 
 
 
• Evidence of endocardial involvement 
 
○ Positive echocardiogram 
 
▪ Oscillating vegetation
 
▪ Abscesses
 
▪ Valve perforation
 
▪ New partial dehiscence of prosthetic valve
 
 
 
○ New valvular regurgitation
 
 
 

Minor Clinical Criteria	
 
• Predisposing heart condition: MVP, bicuspid aortic valve, rheumatic or congenital heart disease, intravenous drug use
 
• Fever
 
• Vascular phenomena: Major arterial emboli, septic pulmonary emboli, mycotic aneurysm, intracranial hemorrhage, Janeway lesions
 
• Immunologic phenomena: Glomerulonephritis, Osler's nodes, Roth spots, and rheumatoid factor
 
• Positive blood culture: not meeting major criteria
 
• Echocardiogram: positive but not meeting major criteria
 

**Note: Clinical Diagnosis of Endocarditis is based on:**

- 2 major criteria; or
- 1 major + 3 minor criteria; or
- 5 minor criteria

## Guideline Directed Medical Therapy (GDMT)

Guideline Directed Medical Therapy (GDMT) is defined per the ACC/AHA/HFSA Heart Failure Guidelines [83]. GDMT must be documented for a minimum of 30 days prior to intended trial registration and subject must be on appropriate class of medications, which typically include: ACE Inhibitor or Angiotensin II Receptor Blocker, Beta-Blocker, and diuretic as appropriate.

## **Hospitalization (All-cause)**

Admission to inpatient unit or ward in the hospital for at least 24 hours, including emergency department stay. Excludes the index procedure hospitalization as well as hospitalizations planned for pre-existing conditions, unless there is worsening in the baseline condition.

For the purpose of the CIP, overnight stays at nursing home facilities, physical rehab or extended care facilities, including hospice, do not meet the protocol definition of hospitalization. Hospitalizations will be adjudicated by the CEC per the following:

**Hospitalization (Cardiovascular):** Treatment in any inpatient unit or ward in the hospital for at least 24 hours, including emergency department stay for cardiovascular conditions such as heart failure (as defined below), coronary artery disease, acute myocardial infarction, stroke, hypertension, cardiac arrhythmias, cardiomegaly, pericardial effusion, atherosclerosis, peripheral vascular disease and mitral valve reintervention or reoperation.

**Hospitalization (Heart Failure):** Any inpatient unit or ward hospitalization for at least 24 hours including emergency stay that requires treatment for heart failure. This definition also includes any event that meets all of the following criteria:

- Subject has clinical signs and/or symptoms of heart failure, including new or worsening dyspnea, orthopnea, paroxysmal nocturnal dyspnea, increasing fatigue, worsening functional capacity or activity intolerance, or signs and/or symptoms of volume overload.
- Results in intravenous (e.g., diuretic or vasoactive therapy) or invasive (e.g., ultrafiltration, IABP, mechanical assistance) treatment for heart failure.

**Hospitalization (Non-Cardiovascular):** Hospitalizations that are not heart failure or other cardiovascular hospitalizations, as defined in this CIP, will be categorized as non-cardiovascular hospitalizations.

## **Index Procedure**

The procedure in which the Tendyne or Control (MitraClip) device implant is first attempted.

## **Left Ventricular Dysfunction**

Subjects enrolled in the SUMMIT trial should be treated with ICD and/or CRT, as per the following guidelines, prior to subject enrollment in the trial:

- An implantable cardioverter-defibrillator is recommended as secondary prevention to prolong survival in subjects with current or prior symptoms of HF and reduced LVEF who have a history of cardiac arrest, ventricular fibrillation, or hemodynamically destabilizing ventricular tachycardia.
- Implantable cardioverter-defibrillator therapy is recommended for primary prevention of sudden cardiac death to reduce total mortality in subjects with non-ischemic dilated cardiomyopathy or ischemic heart disease at least 40 days post-MI, a LVEF less than or equal to 35%, and NYHA Functional Class II or III symptoms while receiving chronic optimal medical therapy, and who have reasonable expectation of survival with a good functional status for more than 1 year

[figure not shown]
- Subjects with LVEF of less than or equal to 35%, sinus rhythm, left bundle-branch block (LBBB), a QRS duration of  $\geq$  150 ms, and NYHA Functional Class III or ambulatory class IV symptoms despite recommended optimal medical therapy, should receive cardiac resynchronization therapy, with or without an ICD, unless contraindicated

### **Local Site Heart Team**

The Local Site Heart Team must consist of, at a minimum, the cardiothoracic surgeon, interventional cardiologist, and an echocardiographer. Additional members of the heart team may include: other imaging specialists (e.g., CT), heart failure specialists, cardiac anesthesiologists, intensivists, nurses, and social workers.

### **Mitral Regurgitation Etiology**

Defined in **Figure 2**, adapted from the 2017 ACC Expert Consensus Decision Pathway for MR [84].

**Abbreviations:**

LA = left atrial; LV = left ventricular;  
LVEF = left ventricular ejection fraction  
MR = mitral regurgitation

**Figure 2. Decision Tree for Determining MR Etiology**

### Modified Rankin Scale Score

The modified Rankin Scale (mRS) will be used to classify strokes as “disabling” or “non-disabling” and should be assessed at the following time intervals:  $\leq 7$  days following an event, at 30 days, and at 90 days.

Score	Definition
0	No symptoms at all
1	No significant disability despite symptoms; able to carry out all usual duties and activities
2	Slight disability; unable to carry out all previous activities, but able to look after own affairs without assistance
3	Moderate disability; requiring some help, but able to walk without assistance
4	Moderately severe disability; unable to walk without assistance and unable to attend to own bodily needs without assistance
5	Severe disability; bedridden, incontinent and requiring constant nursing care and attention
6	Dead

**Disabling stroke:** an mRS score  $\geq 2$  with an increase in  $\geq 1$  mRS category from a subject’s pre-stroke baseline at 90 days.

**Non-disabling stroke:** an mRS score of  $< 2$  at 90 days or one that does not result in an increase in at least one mRS category from an individual’s pre-stroke baseline

### Mitral Valve Academic Research Consortium (MVARC)

The following MVARC endpoints will be captured for the Tendyne device and Control group in the study cohorts [72].

MVARC (Tendyne)	MVARC (Control Group)

Technical Success
 
Measured at exit from procedure room:
 
 
1) Absence of procedural mortality; and
 
2) Successful access, delivery and retrieval of the device delivery system; and
 
3) Successful deployment and correct positioning of the intended device; and
 
4) Freedom from emergency surgery or reintervention related to the device or access procedure
 
 
Note: Criterion #3 above has been modified from the MVARC guidelines since the Tendyne device is designed to be fully retrievable, and thus allows the use of
	
Technical Success
 
Measured at exit from operating room:
 
 
1) Absence of procedural mortality; and
 
2) Successful access, delivery and retrieval of the device delivery system; and
 
3) Successful deployment and correct positioning of the intended device; and
 
4) Freedom from emergency surgery or reintervention related to the device or access procedure
 
 
Note: Criterion #3 above has been modified from the MVARC guidelines as either a single or multiple MitraClip devices may be attempted and/or

MVARC (Tendyne)	MVARC (Control Group)
additional devices during the index procedure.	ultimately implanted, and thus allows the use of additional devices during the index procedure.

Device Success
 
Measured at 30 days and at all later post-procedural intervals:
 
 
1) Absence of procedural mortality or stroke; and
 
2) Proper placement and positioning of the device
 
3) Freedom from unplanned surgical or interventional procedures related to the device or access procedure; and
 
4) Continued intended safety and performance of the device, including:             
 
a) No evidence of structural or functional failure
 
b) No specific device-related technical failure issues or complications
 
c) Reduction of MR to either optimal* or acceptable levels without structural valve dysfunction (see Appendix II: Definitions), and with no greater than mild (1+) paravalvular MR (and without associated hemolysis).
 
 
 
 
Note: Criterion #4c above has been modified from the MVARC guidelines, to align with the structural valve dysfunction definition used in this CIP.
	
Device Success
 
Measured at 30 days and at all later post-procedural intervals:
 
 
1) Absence of procedural mortality or stroke; and
 
2) Proper placement and positioning of the device
 
3) Freedom from unplanned surgical or interventional procedures related to the device or access procedure; and
 
4) Continued intended safety and performance of the device, including:             
 
a) No evidence of structural or functional failure
 
b) No specific device-related technical failure issues or complications.
 
c) Reduction of MR to either optimal* or acceptable levels without significant mitral stenosis (i.e., post-procedure EOA is <math>>1.5 \text{ cm}^2</math>) with a transmитral gradient <math><5 \text{ mm Hg}</math>.
 
 
 
 
Note: Criterion #4c above has been modified from the MVARC guidelines, as paravalvular leak is not applicable to MitraClip.


Procedural Success
 
All of the following must be present (measured at 30 days):
 
 
1) Device success (either optimal or acceptable*); and
 
2) Absence of major device or procedure related serious adverse events, including:             
 
a) Death
 
b) Stroke
 
c) Life-threatening bleeding (MVARC scale)
 
 
 
	
Procedural Success
 
All of the following must be present (measured at 30 days):
 
 
1) Device success (either optimal or acceptable*); and
 
2) Absence of major device or procedure related serious adverse events, including:             
 
a) Death
 
b) Stroke
 
c) Life-threatening bleeding (MVARC scale)
 
 
 

MVARC (Tendyne)	MVARC (Control Group)

 
d) Major vascular complications
 
e) Major cardiac structural complications
 
f) Stage 2 or 3 acute kidney injury (includes new dialysis)
 
g) Myocardial infarction or coronary ischemia requiring PCI or CABG
 
h) Severe hypotension, heart failure, or respiratory failure requiring intravenous pressors or invasive or mechanical heart failure treatments such as ultrafiltration or hemodynamic assist devices, including intra-aortic balloon pumps or left ventricular or biventricular assist devices, or prolonged intubation for <math>\geq 48</math> hours.
 
i) Any structural valve dysfunction, migration, thrombosis, or other complication requiring surgery or repeat intervention.
 
	
 
d) Major vascular complications
 
e) Major cardiac structural complications
 
f) Stage 2 or 3 acute kidney injury (including new dialysis)
 
g) Myocardial infarction or coronary ischemia requiring PCI or CABG
 
h) Severe hypotension, heart failure, or respiratory failure requiring intravenous pressors or invasive or mechanical heart failure treatments such as ultrafiltration or hemodynamic assist devices, including intra-aortic balloon pumps or left ventricular or biventricular assist devices, or prolonged intubation for <math>\geq 48</math> hours
 
i) Any device detachment, migration, thrombosis, or other complication requiring surgery or repeat intervention.
 
 
Note: Criterion #2i above has been modified from the MVARC guidelines as structural valve dysfunction is not applicable to MitraClip.


Patient Success
 
All of the following must be present (measured at 12 months):
 
 
1) Device success (either optimal or acceptable*); and
 
2) Subject returned to the pre-procedural setting; and
 
3) No re-hospitalizations or reinterventions for the underlying condition (e.g., mitral regurgitation, heart failure); and
 
4) Improvement from baseline symptoms (NYHA improvement by <math>\geq 1</math> Functional Classification); and
 
5) Improvement from baseline in functional status (6MWD improvement by <math>\geq 50</math> meters); and
 
6) Improvement from baseline in Quality of Life (KCCQ improvement by <math>\geq 10</math> points).
 
	
Patient Success
 
All of the following must be present measured at 12 months):
 
 
1) Device success (either optimal or acceptable*); and
 
2) Subject returned to the pre-procedural setting; and
 
3) No re-hospitalizations or reinterventions for the underlying condition (e.g., mitral regurgitation, heart failure); and
 
4) Improvement from baseline symptoms (NYHA improvement by <math>\geq 1</math> Functional Classification); and
 
5) Improvement from baseline in functional status (6MWD improvement by <math>\geq 50</math> meters); and
 
6) Improvement from baseline in quality of life (KCCQ improvement by <math>\geq 10</math> points).
 

MVARC (Tendyne)	MVARC (Control Group)

*MR reduction is considered optimal when post-procedure MR is reduced to trace or absent. MR reduction is considered acceptable when post-procedure MR is reduced by at least 1 class or grade from baseline and to no more than moderate (2+) in severity.
	

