### **3.6.2 MVARC Endpoints**

The following MVARC endpoints will be captured for the Tendyne device and Control group in the Randomized, Non-repairable and Severe MAC cohorts (see **Appendix II: Definitions**) [72]:

- Technical Success
- Device Success
- Procedural Success
- Patient Success

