### **5.2.2 Inclusion Criteria**

Subjects must meet all of the following inclusion criteria to participate in the trial:

1. Symptomatic, moderate-to-severe or severe mitral regurgitation (MR  $\geq$  Grade III per American Society of Echocardiography criteria), or severe mitral annular calcification (MAC), where a transcatheter therapy is deemed more appropriate than open surgery by the local site heart team.

**Note:** MR and MS severity must be determined by assessment of a qualifying transesophageal echocardiogram (TEE) and transthoracic echocardiogram (TTE), obtained within 120 days prior to subject consent, and must be confirmed by the Echocardiography Core Laboratory.

**Note:** Patients with severe MAC must have symptomatic mitral valve disease associated with MR $\geq$  Grade III, or severe mitral stenosis (MS), or both moderate MR and moderate MS as assessed by the Echocardiography Core Laboratory.

2. NYHA Functional Classification  $\geq$  II (if Class IV, patient must be ambulatory).
3. The local site heart team determines that the subject has been adequately treated per applicable standards for coronary artery disease (e.g., revascularization), left ventricular dysfunction (e.g., cardiac resynchronization therapy) and heart failure (e.g., GDMT). The SEC must concur that the subject has been adequately treated.
4. The local site heart team and the SEC concur on the intended study cohort for the subject.

**Randomized cohort:** Eligibility for this cohort is limited to subjects where the local site heart team deems the mitral valve anatomy is suitable for TEER and are within approved MitraClip indications, which must be confirmed by experienced MitraClip operators within the SEC. Subjects with primary MR must be at prohibitive surgical risk, while subjects with secondary MR must be symptomatic despite maximally-tolerated guideline-directed medical therapy and meet the MitraClip Indications for Use.

**Non-repairable cohort:** Eligibility for this cohort is limited to subjects where the local site heart team deems the mitral valve anatomy is not suitable for TEER with MitraClip or does not meet MitraClip indications, which must be confirmed by experienced MitraClip operators from the SEC.

**Severe MAC cohort:** Eligibility for this cohort is limited to subjects where the local site heart team deems the degree of MAC renders the subject unsuitable for mitral valve surgery.

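### A Severe MAC or CAP subject who enters for stenosis with mild MR and still has mild MR afterwards fails MVARC Device Success by definition, and so fails Procedural and Patient Success

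*Protocol*

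**What the plan says.** **Entry.** Protocol 5.2.2, inclusion criterion 1 (second note), lets a severe MAC subject qualify on MR of Grade III or more, "or severe mitral stenosis (MS), or both moderate MR and moderate MS as assessed by the Echocardiography Core Laboratory". The stenosis route carries no MR minimum. CAP eligibility is stated to be identical.

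**Where the measures apply.** Protocol 3.6.2 has the MVARC measures "captured for the Tendyne device and Control group in the Randomized, Non-repairable and Severe MAC cohorts". SAP Appendix VI (VI.1.4.3.2) lists the same four measures for the CAP and refers to the definitions in Protocol Appendix II.

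**The rule.** Tendyne Device Success criterion 4c calls for "Reduction of MR to either optimal* or acceptable levels without structural valve dysfunction", "and with no greater than mild (1+) paravalvular MR (and without associated hemolysis". The footnote to the tables defines optimal as trace or absent MR after the procedure. For the alternative, "MR reduction is considered acceptable when post-procedure MR is reduced by at least 1 class or grade from baseline", and MR must also be no worse than moderate (2+).

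**What depends on it.** Procedural Success (30 days) and Patient Success (12 months) both have as their first condition "Device success (either optimal or acceptable*); and". Device Success is scored at 30 days and again at every later interval.

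**Status.** SAP 3.5.2 reports the MVARC measures with descriptive statistics only.

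**The concern.** The footnote judges success by the change in MR. That suits a subject enrolled for regurgitation. It does not suit one enrolled for stenosis whose MR was only mild to begin with: unless MR goes to trace or absent, there is no grade left to fall that would count. The Tendyne 4c wording has no alternative for such a subject, and the SAP adds none.

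At stake is the meaning of three reported success rates in Severe MAC and CAP. Some failures would come from how the rule treats the entry lesion. The CAP results are to be set beside those of the Severe MAC cohort (Protocol 10.2.4) and may support the marketing application, so a difference in the share of stenosis entrants between the two could move the rates a little for reasons of definition.

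**Working it through.** The plan states no rate, power or sample size for the MVARC measures, so there is no figure to reproduce. The check is to apply the footnote to each combination of grades.

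**Step 1. Rule.** Optimal: post-procedure MR none or trace. Acceptable: fall of at least one grade and post-procedure MR no more than 2+. Otherwise criterion 4c fails. The paravalvular clause in 4c is joined by *and*; it is a further restriction, not another way to pass.

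| Baseline MR | Post none/trace | Post mild (1+) | Post moderate (2+) |
|---|---|---|---|
| None/trace | optimal | fail | fail |
| Mild (1+) | optimal | **fail** | fail |
| Moderate (2+) | optimal | acceptable | fail |
| Grade III or IV | optimal | acceptable | acceptable |

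Post-procedure Grade III or IV fails from every baseline. A subject with none or trace at baseline cannot literally be reduced to that level; the table reads staying there as optimal.

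**Step 2. Compare with the tested MR endpoint.** Protocol 10.2.3 and SAP 2.3.3.2.1 count MR of mild or less at 30 days as success, whatever the baseline. The whole mild column is therefore a success there, while the footnote splits it by baseline grade. The moderate-plus-moderate entry route is not affected, because a fall from 2+ to mild is acceptable.

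**Step 3. Size of the effect on Device Success.** Expected failures due to the rule = N × s × q, where:
- N = 103 (Protocol 4.2);
- s = share entering for stenosis with mild MR, not in the documents, assumed 10-30%;
- q = share of those left with mild MR, not given for MAC.

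For q, Protocol 2.1.7 reports no more than trace MR in 98.8% of the first Tendyne patients at one month (100 − 98.8 = 1.2% above trace), and Protocol 2.1.8 puts the one-year figure below 2%. That series was not a MAC population. As a pessimistic alternative, q is assumed to be 10-30%.

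| s | q | N × s × q |
|---|---|---|
| 0.10 | 0.012 | 103 × 0.10 × 0.012 = 0.1 |
| 0.30 | 0.02 | 103 × 0.30 × 0.02 = 0.6 |
| 0.10 | 0.10 | 103 × 0.10 × 0.10 = 1.0 |
| 0.30 | 0.30 | 103 × 0.30 × 0.30 = 9.3 |

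As a loss in the Device Success rate this is s × q: from 0.10 × 0.012 = 0.1 points to 0.30 × 0.30 = 9 points.

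**Step 4. The other two measures.** Procedural Success also requires freedom from a list of major events. Patient Success also requires return to the prior setting, no rehospitalization or reintervention for the underlying condition, and gains in NYHA class, walk distance and KCCQ. Some of the subjects in Step 3 would fail on those grounds anyway, so the counts are upper bounds there.

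**The case against.** The strongest reply is that the problem may hardly occur. Tendyne rarely leaves more than trace MR in the sponsor's series, and Protocol 2.1.7 reports complete relief of MR in all nine compassionate-use MAC cases. This stands as a reason to expect the low end. It does not settle the matter: the series was not a MAC population, nine cases are few, and Protocol 2.1.4 cites a MAC registry of other prostheses in which only 62.2% reached trace or none.

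Second, no decision rests on these measures. They carry no hypothesis test, Severe MAC success depends on the primary endpoint, and MR grade is tabulated separately at each echocardiographic time point. All of that stands and limits the importance of the point.

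Third, a reader might find it perverse that a fall from severe to moderate MR passes while mild-to-mild fails. The footnote does read that way, but the route is narrow. Criterion 4c caps paravalvular MR at mild, moderate transvalvular regurgitation counts as moderate hemodynamic dysfunction under the structural valve dysfunction definition, and criterion 4a excludes functional failure. The firmer contrast is that the same mild residual MR passes from 2+ or worse and fails from mild.

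Fourth, a reader might infer that the three rates would reflect lesion mix and not device performance. The documents do not support that. A stenosis subject left with trace or no MR passes as optimal, so a failure still requires residual MR after valve replacement, which is in part a device result.

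**Conclusion.** The point holds as a gap in a definition. An eligible subgroup, with mild MR before and after, is scored a failure on Device Success and hence on Procedural and Patient Success, while the same echo finding is a success on the Severe MAC 30-day MR endpoint.

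Its size cannot be computed from the documents, which give neither the lesion mix nor the residual-mild rate in MAC. With 10-30% of 103 subjects assumed to enter with mild MR, it is under 1 subject at the 1.2-2% rate of the Tendyne series and about 9 if 30% keep mild MR. Those figures apply to Device Success only. It would be wrong to read them as the loss on each of the three measures, because the other two have further conditions that some of the same subjects would fail.

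Nor should a reader infer any threat to cohort success or labeling claims. The primary endpoint, the tested secondary endpoints, alpha, power and sample size are untouched. This is a low-priority correction to descriptive reporting.

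**What to change.** Add to the Appendix II footnote, marked as a modification of MVARC in the way the tables already mark others:

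- baseline core-laboratory MR mild: post-procedure MR of mild or less is acceptable;
- baseline none or trace: optimal if MR stays trace or absent, with any rise to mild reported separately and not counted as an acceptable reduction;
- all other subjects: the one-grade rule and the 2+ ceiling stay as they are.

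For Severe MAC and CAP, report Device, Procedural and Patient Success under both the published and the modified definition, so that comparison with other MVARC reports is kept.

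No new data are needed, because baseline and follow-up MR grades are already read by the core laboratory. The cost is a short addition to the footnote, one more departure from MVARC wording and one extra descriptive table. The change does not add a measure of stenosis relief; it only stops the MR rule from failing subjects who had no more than mild MR to lose.
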